Measurements and procedures:	
45 minutes prior to the first round of imaging, patients and controls provide baseline information on current pain and function (painDetect questionnaire²⁴, Oswestry Disability Index (ODI)²⁵). Additional information is collected on the localization of pain (pain drawing), whether back or leg pain is dominant, and whether there is a preference in movements or activities (e.g. walking, sitting for a long time, rising from sitting, forward bending or standing)^{26,27-29}.
 
Patients and controls then undergo a clinical examination including assessment of blood pressure and pulse, lower extremity neurological examination³⁰, nerve tension tests, active range of motion of the lumbar spine, facet joint provocation test^{31,32}, and palpatory segmental examination of the lumbar spine^{33,34}. In patients, the skin above the interspinous ligament causing the most pain upon palpation by the examiner is marked with pen. A blood sample of approximately 10-15 ml is obtained from participants agreeing to additionally undergo venipuncture by a medical professional trained in venipuncture. This procedure is not mandatory and is agreed to separately in the informed consent form. The examination is followed by a rest period of 10 minutes.
 
Patients and controls are then evaluated in the MRI-Scanner lying supine. Upon completion of this scan, patients will be randomized either to receive either a total of two spinal manipulative interventions, first in right, then left side-lying position at the segment of the marked interspinous ligament, or receive only pre-SMT positioning by the chiropractor administering the intervention, who places his/her hand on the site of the marked skin above the interspinous ligament without applying pressure, preload or thrust in right and left side-lying position.
 
For patients, three sequential post intervention MRIs are performed immediately after the intervention. Once imaging is complete, the patients exit the scan room and provide post-intervention information on current pain-intensity. Blood pressure and pulse are reassessed. Patients will be contacted after 1 week, 1 month and 3 months and follow-up data will be collected on pain and disability.
 
Controls are reassessed in a second MRI after 20 minutes of supine lying to assess the repeatability of IVIM imaging, and will undergo a third imaging sequence approximately 10 hours later (after partaking in activities of daily life as normal, but excluding strenuous physical activity) in order to assess diurnal changes in perfusion and diffusion parameters on IVIM and DWI imaging. This scan will serve as a positive control that diurnal changes in diffusion parameters described in the nucleus pulposus can be detected³⁵.

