3.6 Explanation for choice of comparator (or placebo)

The intervention and control procedure differ only in the administration of a high-velocity, low-amplitude SMT intervention for the intervention group. The control procedure therefore is chosen to be identical to the intervention procedure with the exception that tissue pressure and thrust are not administered to the spinal segment. This ensures that there is minimal confounding due to position changes and human touch.

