10.1 Hypothesis

Intervertebral discs and adjacent spinal muscle tissue of the lumbar spine will show a change in the apparent diffusion coefficient and perfusion coefficient on MRI after an SMT intervention.

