10.2 Determination of Sample Size

N = 70 (25 per patient group, 20 controls). Rationale: Based on the study results by Wong et al.¹⁸, we expect an increase in ADC values of at least 6.5% (CI: 3.88%-9.13%) in receivers of SMT-intervention compared to no change in the control-intervention group. 25 patients per group will provide a power of 0.8 (1-beta) to detect an effect of 0.9 at an alpha-level of 0.05⁴⁸. Additionally, the repeatability of IVIM-MRI on musculoskeletal tissue will be assessed in 20 control subjects.

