10.3 Planned Analyses

Distributions of the ADC and perfusion coefficient obtained at the two time points (before and after intervention) will be tested for the assumptions of normality using the Shapiro-Wilk test. In case of non-normality, data transformation will be used to normalize data. Should this not be possible, non-parametric tests will be used. Two separate repeated measures analysis of variance (ANOVA) will be used to test for effects of time (pre- vs. post-intervention) on ADC and perfusion coefficients with intervention (experimental vs. control intervention) and group (degenerated vs. non-degenerated painful segments) as between-subject variables.

We will estimate the repeatability of IVIM-MRI in measuring perfusion in musculoskeletal tissue using paired t-tests and the intraclass correlation coefficient ICC⁴⁹.

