10.3.2 Primary Analysis

Our hypothesis is that a spinal segment receiving an SMT-intervention will show a change in the diffusion and pseudodiffusion coefficient that is significantly higher than a spinal segment receiving a control intervention. Distributions of the ADC and perfusion coefficient obtained before and after intervention will be tested for the assumptions of normality using the Shapiro-Wilk test. In case of non-normality, data transformation will be used to normalize data. Should this not be possible, non-parametric tests will be used. Two separate repeated measures analysis of variance (ANOVA) will be used to test for effects of time (pre- vs. post-intervention) on ADC and perfusion coefficient with intervention (experimental vs. control intervention) and group (degenerated vs. non-degenerated painful segments) as the between-subject variables.

The PI will supervise the primary analysis as described above. It will be analyzed using SPSS (version 23) at the end of the recruitment period and after obtaining all necessary data.

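### The primary ANOVA names only the effect of time as tested; the SMT-minus-control contrast is not named as deciding, and the post-intervention scan is not fixed

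*Combined protocol and SAP*

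**What the plan says.** **The test.** Sections 10.3 and 10.3.2 both plan two separate repeated-measures ANOVAs, one for ADC and one for the perfusion coefficient. The stated purpose in 10.3.2 is "to test for effects of time (pre- vs. post-intervention) on ADC and perfusion coefficient with intervention (experimental vs. control intervention) and group", where group means degenerated or non-degenerated painful segments. Neither section mentions an interaction, a difference in change, or the term that decides success. If transformation fails, unspecified non-parametric tests are used.

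**The hypothesis.** The first sentence of 10.3.2 is between-arm: the SMT segment will show a "change in the diffusion and pseudodiffusion coefficient that is significantly higher than a spinal segment receiving a control intervention". Section 10.2 sizes the trial on the same contrast, an ADC increase "in receivers of SMT-intervention compared to no change in the control-intervention group", and says that 25 per group "will provide a power of 0.8 (1-beta) to detect an effect of 0.9". Section 10.1 has no comparator: the tissues "will show a change in the apparent diffusion coefficient and perfusion coefficient on MRI after an SMT intervention".

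**The post value.** Section 10.3 speaks of values "obtained at the two time points (before and after intervention) will be tested for the assumptions of normality". The synopsis (Measurements and procedures) and 5.1 give patients three sequential scans after the intervention. Section 8.3.2 describes one second round of imaging. The study schedule has one post-intervention MRI mark for patients, in the +5 column. No section says whether the first, the last, the mean or all of the scans supply the post value.

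**The concern.** Section 3.6 justifies the control intervention as ensuring "minimal confounding due to position changes and human touch". Only a comparison of the arms uses that protection. A main effect of time averages the change over both arms, so anything that moves both arms together (repositioning, lying down, scanner drift, time of day) counts towards it.

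The protocol itself expects disc diffusion to move without SMT. The third scan in asymptomatic controls is there to show that "diurnal changes in diffusion parameters described in the nucleus pulposus can be detected". That interval is about 10 hours, and the documents give no figure for the much shorter gap between a patient's pre and post scans.

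Two choices are left open: which model term decides, and which scan is the post value. If either is settled once output is available, the 5% error rate is no longer assured. The unnamed non-parametric fallback adds a third gap, since nothing requires it to compare the randomised arms.

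**Working it through.** **Inputs.** From 10.2: 25 per arm, effect 0.9, alpha 0.05, power 0.8. Assumed because not stated: 0.9 is a standardised between-arm difference in change, the test is two-sided, and there is no dropout. The SD of change is set to 1. With two time points, time-by-intervention is a two-sample comparison of change scores, and time is a test that the average change over both arms is zero.

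**1. The plan's own figure.** Noncentrality = 0.9 × √(25/2) = 3.18 on 48 df, giving power 0.877, not 0.80; 21 per arm would give 0.80. The stated power is therefore conservative on this reading. That mismatch is a separate matter, but it shows that naming the arm contrast needs no larger sample.

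**2. A shift shared by both arms, no SMT effect.** For time, noncentrality = shift × √50, on 46 df with degeneration and its product with intervention in the model. The shifts are assumed.

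| Shared shift (SD of change) | Noncentrality | Time significant | Time-by-intervention significant |
|---|---|---|---|
| 0.05 | 0.35 | 6% | 5% |
| 0.1 | 0.71 | 11% | 5% |
| 0.2 | 1.41 | 28% | 5% |
| 0.3 | 2.12 | 55% | 5% |
| 0.5 | 3.54 | 93% | 5% |

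Simulation of the factorial model (100,000 replicates) agrees at 0.2, 0.3 and 0.5: 28.3%, 54.6% and 93.2%.

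**3. Whether time can identify an SMT effect.** If SMT moves by 0.9 and control by 0, the average is 0.45 and noncentrality is 0.45 × √50 = 3.18. If both arms move by 0.45, the average and noncentrality are the same. Time is significant in 88% of trials in both cases; time-by-intervention is significant in 88% and 5%. This result needs no assumption about how large a shared shift really is.

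**4. The post scan.** With no effect, suppose the most favourable of three post scans were taken at 5%. Two-sample t tests on change (100,000 replicates), with assumed correlations between the scans' change scores of 0.9, 0.7 and 0.5, give 8.4%, 11.0% and 12.8% error.

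**5. Gain from baseline adjustment.** With equal pre and post variance and correlation ρ, and SD of change 1, the residual SD after adjusting for baseline is √((1+ρ)/2). The effect of 0.9 becomes 0.9/0.866 = 1.04 at ρ = 0.5, 0.9/0.922 = 0.98 at 0.7, and 0.9/0.975 = 0.92 at 0.9. Simulated power with additive degeneration is about 94%, 92% and 88%, against 88% unadjusted.

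**6. Supporting point: the product term.** In a full factorial with Type III tests, the arm contrast weights degenerated and non-degenerated segments equally. With k of 25 degenerated per arm, its variance is ½(1/k + 1/(25−k)).

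| Assumed split | k | Variance | Noncentrality (0.9/√variance) | Power |
|---|---|---|---|---|
| 60:40 | 15 | 0.0833 | 3.12 | 86% |
| 72:28 | 18 | 0.0992 | 2.86 | 80% |
| 80:20 | 20 | 0.1250 | 2.55 | 70% |

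Additive degeneration without the product gives about 88% at the 72:28 and 80:20 splits. This assumes the same SMT effect in both kinds of segment.

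**The case against.** The strongest reply is that the plan already makes the right comparison. The between-arm hypothesis opens the same paragraph as the ANOVA, intervention is a factor in the model, and the sample size uses the same contrast. Effects of time, in the plural, with between-subject factors can be shorthand for all within-subject effects, including time-by-intervention. Most of this stands: the model is not wrong and the intended reading is fairly clear. It does not close the gap, because 10.1 drops the comparator and no sentence says which term decides.

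A reader might infer that a significant time effect alone would be declared a success, or that either term would do (about 9.7% error with no change in either arm), or that the best of three scans may be picked. The documents support none of these; no section permits such a rule. The percentages show what the silence would allow, not what the plan prescribes.

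The shared shift may also be negligible. The scans are minutes apart at morning visits, 10.2 assumes no change in the control arm, and at 0.05 SD the excess error is only about one percentage point. That is fair, and is why the table starts there.

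The scan descriptions can be partly reconciled: one second round could contain three acquisitions, and the +5 mark could be the start of post-scanning. The separate rounds in 5.1 resist this, and the rule for the post value would still be missing.

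The degeneration splits and the pre-post correlations are assumptions. ANCOVA is a better choice, not the repair of an error.

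**Conclusion.** The point holds as a gap in specification that should be closed before data are seen. The plan names an effect that does not test its own hypothesis, names no deciding term, and does not define the post value. That time cannot tell an SMT effect from a shared shift follows from the model and rests on no assumed shift. The size of the consequence is not known from the documents: it runs from about 6% to 93% false positives over assumed shifts of 0.05 to 0.5 SD if time were used, and about 8% to 13% if the scan were chosen on results, for assumed correlations of 0.9 to 0.5. It does not follow that the ANOVA is invalid or that the trial is underpowered; the arm contrast has about 88% power at the stated effect. The loss from the product term is a supporting point only. The success rule across the several parameters and tissues in 4.1 is a separate issue that this point does not settle.

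**What to change.** - **Name the test.** State in 10.1, 10.3 and 10.3.2 that the primary test is the SMT-minus-control-intervention difference. Preferably estimate it with a 95% CI by ANCOVA of the post value on intervention, baseline value, the randomisation strata actually used, and degeneration as an additive covariate. At minimum, name time-by-intervention as deciding.
- **Fix the post value.** State in advance which post-intervention scan, or the mean of the three, is used. Reconcile the synopsis and 5.1 with the schedule, 8.3.2 and 10.3.
- **Fallback and descriptive results.** Require any non-parametric fallback to compare the randomised arms. Report the time main effect and within-arm changes as descriptive.
- **Degeneration.** Test intervention-by-degeneration in its own named model. Reconcile its status: the synopsis puts it in the main objective, 3.11 makes it secondary.
- **Strata.** Reconcile 5.2.1 (age and sex) with 6.3 (age, sex and degenerative changes).

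The cost is wording and a few degrees of freedom, with no new data. If degeneration is a stratum, it must be graded between the first scan and randomisation. Section 5.1 describes that viewing only as a contraindication screen, so the sponsor must confirm that grading is feasible then.

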10.3.3 Secondary Analyses

We will estimate the repeatability of IVIM-MRI in measuring perfusion in musculoskeletal tissue using paired t-tests and the intraclass correlation coefficient ICC⁴⁹.

The PI will supervise the secondary analysis as described above. It will be analyzed on SPSS (version 23) at the end of the recruitment period and after obtaining all necessary data.

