
Objectives:	
The main objective of this study is to quantify changes in diffusion and perfusion in the intervertebral disc and adjacent spinal muscle tissue of a spinal segment receiving SMT or control intervention and to evaluate whether those changes differ in spinal segments with or without degenerative changes in low back pain patients.
 
The second study objective is to evaluate the repeatability of IVIM-MRI for quantifying perfusion changes in musculoskeletal tissues and to assess diurnal changes in perfusion and diffusion parameters in spinal tissues as a positive control.

Outcomes:	
The primary study outcome is the change in diffusion (ΔADC) and perfusion (Δ perfusion fraction, Δ pseudodiffusion coefficient) parameters measured on DWI and IVIM MRI in the intervertebral disc and adjacent spinal muscle tissue of a lumbar spinal segment following a lumbar SMT or control intervention to that segment, or, for controls, after 20 minutes of lying in supine resting position.
 
Secondary outcomes are the repeatability and diurnal changes of diffusion- and perfusion-weighted MRI parameters in musculoskeletal tissue in controls, the severity of degenerative changes classified according to the Pfirrmann- and Weishaupt-Classification on MRI, clinical baseline parameters, pro- and anti-inflammatory markers in the obtained blood samples and changes in pain intensity on a numerical pain rating scale after the intervention.

Study design:	Randomized controlled clinical trial

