3.8 Justification of choice of study population

Patients included in this study are persons over 18 years and below 75 years of age with low back pain of a duration of more than 4 weeks clinically not attributable to “red flags” (i.e., infection, trauma, fractures, inflammatory spondylarthropathies). This corresponds to the patient population typically treated in chiropractic practices in Switzerland⁴⁶. Controls are healthy participants over 18 and below 75 years of age who have not suffered from low back pain in the last year and have never experienced low back pain for longer than 7 consecutive days. Patients and controls provide informed consent before inclusion into the study. No vulnerable participants will be included in this study. Study Objective

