3.11 Secondary Objectives

Secondary objectives are to determine if diffusion and perfusion changes in DWI and IVIM-MRI are dependent on the severity of degenerative changes classified according to the Pfirrmann- and Weishaupt-Classification; to establish the relationship between clinical baseline parameters and diffusion and perfusion changes in DWI and IVIM-MRI and to determine the repeatability of IVIM-MRI in assessing perfusion changes, as well as assessing diurnal changes in perfusion and diffusion parameters in spinal tissues of healthy controls. Additionally, the presence of several pro- and anti-inflammatory markers in blood will be assessed in patients and controls.

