4. STUDY OUTCOMES

4.1 Primary Outcome

Changes in diffusion in intra- and extracellular compartments (D), apparent diffusion coefficient (ADC), perfusion in capillaries (D^*) and volume fraction of capillary perfusion (f) in the intervertebral disc and adjacent spinal muscle tissue in patients before and after an SMT- or control intervention and in controls before and after 20 minutes of lying supine.

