4.2 Secondary Outcomes

Secondary outcomes are the repeatability and diurnal changes of diffusion- and perfusion-weighted MRI parameters in musculoskeletal tissue in controls.

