6.2 Recruitment and screening

Patients will be recruited from within the Department of Chiropractic Medicine at the University Hospital of Balgrist.

Asymptomatic controls will be recruited by flyers displayed on the hospital's internal website (intranet) and notice boards.

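### IVIM repeatability is to be judged only by paired t-tests and an ICC; the plan does not commit to reporting the absolute scan-to-scan error

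*Combined protocol and SAP*

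**What the plan says.** The synopsis (Objectives) gives repeatability the rank of a study objective: "The second study objective is to evaluate the repeatability of IVIM-MRI for quantifying perfusion changes in musculoskeletal tissues". Section 3.11 repeats it as a secondary objective, "to determine the repeatability of IVIM-MRI in assessing perfusion changes", and section 4.2 lists as secondary outcomes the "repeatability and diurnal changes of diffusion- and perfusion-weighted MRI parameters in musculoskeletal tissue in controls".

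The data are two scans of each of 20 pain-free controls, separated by about 20 minutes of supine rest (synopsis, 5.1, 8.3.2, 10.2). Section 3.8 describes this group: "Controls are healthy participants over 18 and below 75 years of age". On their source, section 6.2 says: "Asymptomatic controls will be recruited by flyers displayed on" the hospital intranet and notice boards. No quota for age or disc degeneration is set for them.

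The analysis is stated twice in the same words. Section 10.3.3 reads: "We will estimate the repeatability of IVIM-MRI in measuring perfusion in musculoskeletal tissue using paired t-tests and the intraclass correlation coefficient". Section 10.3 also has "using paired t-tests and the intraclass correlation coefficient". A reference on method-agreement analysis is cited there. The ICC form, a confidence interval and an acceptance threshold are not given. No section names a within-subject SD or CV, a repeatability coefficient or limits of agreement.

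**The concern.** Repeatability asks how far two scans of an unchanged person differ. The two planned measures answer other questions.

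- The paired t-test asks whether the mean moved between scans. Random error enters only its denominator, so a noisier method makes a reassuring non-significant result more likely when a real shift exists, and no less likely when none does.
- The ICC asks what share of the total variance lies between people. It does fall as noise rises if the spread between people is held fixed. Here that spread is set by whoever answers the flyer, over an age range of more than 50 years. An ICC from this sample need not carry over to a sample with a different spread.

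Followed as written, the plan could report no significant difference and a good ICC, and still not tell the reader the measurement error in the units of each parameter.

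There is also a mismatch of scope. Sections 10.3 and 10.3.3 cover perfusion only, while section 4.2 and the synopsis outcomes include repeatability of the diffusion parameters.

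**Working it through.** The plan states no target or expected figure for repeatability, so there is none to reproduce. The only inputs from the documents are 20 controls and two scans each. **All SDs below are assumptions**, expressed as a percentage of the parameter mean. They are not compared with the 6.5% in section 10.2, which is an expected group-mean ADC change; a repeatability coefficient is a limit for one person.

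**Formulas**, with s_w the within-subject and s_b the between-subject SD:
- ICC = s_b² / (s_b² + s_w²)
- Repeatability coefficient RC = 1.96 × √2 × s_w = 2.77 × s_w
- SD of differences = √2 × s_w

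**1. Same ICC, different error**

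| s_w | s_b | ICC | RC |
|---|---|---|---|
| 2.5% | 5% | 25/31.25 = 0.80 | 6.9% |
| 5% | 10% | 100/125 = 0.80 | 13.9% |
| 10% | 20% | 400/500 = 0.80 | 27.7% |

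**2. Same error, different ICC.** With s_w = 5% the RC is 13.9% throughout. For s_b of 2.5%, 5%, 10% and 20% the ICC is 0.20, 0.50, 0.80 and 0.94.

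**3. Evidence in the ICC's favour.** With s_b fixed at 20%, and s_w of 5%, 10%, 20% and 30%, the ICC falls: 0.94, 0.80, 0.50, 0.31. At a fixed spread it does register noise.

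**4. Precision with 20 pairs**
- Observed ICC of 0.80: F = (1 + 0.80)/(1 − 0.80) = 9, and the 97.5% point of F on 19 and 19 df is 2.53. The lower limit is (9/2.53 − 1)/(9/2.53 + 1) = 0.56 and the upper limit is (9 × 2.53 − 1)/(9 × 2.53 + 1) = 0.92.
- RC: the 95% CI is the estimate times √(19/32.85) = 0.76 to √(19/8.91) = 1.46. So 6.9% has a CI of 5.3% to 10.1%, and 27.7% has a CI of 21.1% to 40.5%.

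**5. What the t-test can see (n = 20, two-sided 5%)**
- It has 80% power for a mean shift of 0.66 SD of differences, which is 0.66 × √2 = 0.93 within-subject SD. The detectable shift therefore grows in proportion to the noise. This step assumes only normal differences.
- The smallest observed shift that reaches significance is 2.093 × √2 × s_w / √20. That is 1.7% for s_w = 2.5% and 6.6% for s_w = 10%.
- For an illustrative true shift of 3%, power falls from 95% to 15% between those two noise levels.

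**6. Simulation of the planned pair of measures.** I used 20,000 runs for each row of the table in step 1, with no true shift. The t-test was non-significant in 94.9%, 94.8% and 95.4% of runs. The median absolute-agreement ICC was 0.80 in all three (5th to 95th percentile about 0.61 to 0.90). The median estimated RC was 6.8%, 13.6% and 27.3%. The two planned measures cannot tell the three situations apart; the RC can.

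**The case against.** The strongest reply is that nothing is lost. The paired t-test already computes the SD of differences, so the absolute error can be derived whenever someone wants it. The ICC falls with noise within a given sample. The plan sets no pass rule that could mislead, and the primary comparison is untouched. That is all true, and it limits the weight of the point. What remains is that the plan names its measures for a stated objective and none of them is the error itself.

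The fourfold contrast between 6.9% and 27.7% is built in by the assumed spreads of 5% and 20%. That is so. At a fixed ICC the RC is proportional to s_b, so another pair of spreads would give another ratio. The conclusion does not rest on the particular values, only on the spread being unfixed by the design.

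The cited method-agreement reference may suggest that agreement methods were intended. A citation without a named measure does not commit the analyst to one.

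A systematic shift between scans does bear on stability over the 20 minutes, so the paired comparison has a proper use. It should be kept for that, and labelled so.

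Some technical reservations stand as qualifications. The interval in step 4 is the consistency form; the one-way form gives 0.57 to 0.92, so little changes. The 19 df hold for each parameter and region with one value per control. Because controls leave the scanner and re-enter, the differences include repositioning and any physiological change, not scanner noise alone.

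**Conclusion.** The point holds. For a stated objective and secondary outcome, the plan commits to one measure that does not assess random error and one that expresses it only relative to the spread in a volunteer sample. On the assumed values, an ICC of 0.80 is compatible with a repeatability coefficient anywhere from 6.9% to 27.7%, and one fixed error (13.9%) with an ICC anywhere from 0.20 to 0.94. These ranges rest on assumed SDs, since the documents give none. The behaviour of the t-test does not depend on them. The change should be made, but it concerns the repeatability objective only and does not touch the randomised comparison.

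**What to change.** In sections 10.3 and 10.3.3, for each parameter and region with one value per control:

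- **Main measures:** within-subject SD (SD of differences / √2, or a CV from the log scale if error grows with the mean) and the repeatability coefficient (2.77 × within-subject SD), each with a 95% CI.
- **Plot:** a Bland-Altman plot with mean difference and limits of agreement, mainly to check whether error grows with the mean. The half-width of the limits equals the coefficient, so it is not a second estimate.
- **Scope:** diffusion as well as perfusion parameters, to match section 4.2.
- **ICC:** keep as supplementary, absolute-agreement form, with CI. State that this form counts a mean shift as error, while the within-subject SD above removes it.
- **Paired mean difference with CI** (and the t-test, if wanted): keep as the estimate of systematic change, not as evidence of repeatability. This use is needed, because section 4.1 makes the change "in controls before and after 20 minutes of lying supine" part of the primary outcome and the ANOVA in 10.3 and 10.3.2 covers only the two patient arms.
- If patients' individual changes are set against the coefficient, do so descriptively. Note that it comes from pain-free controls who only rested supine, whereas patients are turned to both sides.

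The cost is analysis and reporting wording. The same 20 scan pairs suffice, and the key quantity is already computed inside the t-test.
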